Iron and erythropoietin are linked by each playing a role in the oxygen sensing pathway regulated by hypoxia inducible factor (HIF). We know that HIF plays a key role in sensing low oxygen, and thus plays a key role regulating human's response to low oxygen during acute and chronic exposure to high altitude. By using these compounds to modulate the HIF pathway we propose to discover the most important components of the pathway for overcoming hypoxia exposure in healthy, fit humans.

B. Specific Aims/Study Objectives

The overarching goal of the study is to determine the effect of iron and erythropoietin (EPO) supplementation on acute and chronic physiological responses to high altitude.

[figure not shown]
Specific aims

1. To determine the effects of iron and EPO on exercise performance acutely (first 3 days), during acclimatization (days 7-8), and chronically (days 13-14) at altitudes of 10,000 to 14,000 feet in PFO- and PFO+ subjects.
2. To determine the effects of iron and EPO on acute and chronic changes in hemoglobin (Hb) mass, cognitive performance, ventilation, and molecular markers of hypoxia exposure at altitudes of 10,000 to 14,000 feet in PFO- and PFO+ subjects.
3. To determine the effects of iron and EPO on development of acute mountain sickness (AMS) at altitudes of 10,000 to 14,000 feet in PFO- and PFO+ subjects.

Please note that all baseline studies will provide novel data on men and women with and without a patent foramen ovale (PFO) so that even if the altitude studies become unfeasible, new information will be gained from these studies.

C. Methods, Materials and Analysis

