Subjects will perform hemoglobin mass (Hb mass) and p50 measures (~75 minutes). This measurement involves placing an IV and drawing an additional 10 mL of venous blood. Any subject with child bearing potential will be required to take a pregnancy test prior to Hb mass testing. In addition, subjects will have baseline venous blood drawn (60 mL of venous blood will be analyzed for various biomarkers and 5 mL for sickle cell screening to be analyzed by QUEST). Dried Blood Spot samples will be taken utilizing a commercially available dried blood spot sampling device (80 uL) (TASSO, Tasso Inc, Seattle, USA). Dried blood will be analyzed for HGB, CD71/Band3, ESAs, and reticulocytes. Total Blood drawn for this day of ~76 mL.

Drug intervention, Eugene, OR

For the 4 weeks immediately prior to the scheduled departure date, subjects will arrive at the Cardiopulmonary Lab as required by their intervention schedule (see 'Drug Intervention' below for details) to receive their assigned intervention via a sub-cutaneous injection and/or intravenous

injection. After the last dose, subjects will have venous blood drawn (~60 mL) prior to departure to Colorado for measurements of various biomarkers. A dried blood drop sample (80 uL) will also be taken.

COLORADO FIELD SITE:

All studies performed in Colorado will happen in laboratory space created by the investigators and/or on running tracks and trails in or very near Leadville or Breckenridge, CO.

Early high-altitude measures: Days 1-3

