hematocrit, baseline proportion of hemoglobin bound with CO (HbCO), and baseline proportion of hemoglobin bound with oxygen (HbO₂). HbCO is typically 1.5 to 2.0% in nonsmoking city dwellers. Once the baseline blood sample has been taken, subjects will be instructed to breathe out completely. Then they take a slow breath from the rebreathe circuit prefilled with 100% oxygen to completely fill their lungs while a bolus of 99.9% pure CO is injected into the circuit. The bolus volume of CO is calculated from body mass (1.0 mL/kg body mass for men; 0.8 mL/kg body mass for women). This dose of CO is expected to raise HbCO by ~6% to ~8%, which is below the levels associated with side effects (>15%; see below). After CO administration the subjects begin breathing normally for 10 minutes. At the end of this 10-minute period, subjects expire all of their air back into the spirometer and the spirometer is sealed and a post-rebreathe blood sample of 2mL is taken to measure the above-mentioned blood parameters (with the exception of p50, which is measured once prior to Hb mass testing). Subjects then goes back to resting while breathing ambient air. Finally, we obtain the total volume of gas in the rebreathe circuit and determine the concentration of CO left in the rebreathe circuit after the test. Using established formulas, we calculate hemoglobin mass and then use the following equations to obtain red cell volume (Red Cell Volume = hemoglobin mass x hematocrit x hemoglobin-1 x 100-1) and then blood volume (Blood Volume = red cell volume x 100 x hematocrit-1 x 0.91-1). Subjects will then repeat the above procedures within 10 minutes after completion. Procedures, including volume of CO injected and blood withdrawn, are identical, with the exception of p50 measurements, which will only be done once prior to CO inhalation. The second test is performed to establish a low test-retest variable as it minimizes biological variation that would occur between days. If these two tests yield results within 3% then the test is complete. If greater than 3% we will repeat the 2 tests on a different day once CO levels in the blood have returned to baseline (~48 hours). In total, 10 mL of blood will be taken (8mL for Hb mass - 4mL for each test, and 2mL for p50). CO level in the blood is not expected to exceed 20% following the second test. If it does, subjects will breathe 100% oxygen for 10 minutes. p50, the partial pressure of oxygen when Hb is 50% saturated with oxygen, is calculated using pre-rebreathe values for pH, PvO₂, PvCO₂, Hb concentration, HbO₂, and HbCO. Hb mass will be measured in this manner, i.e., duplicate tests, at baseline day 6 and on days 1, 7, and 13 at high altitude. p50 will be measured on every day Hb mass is measured, as well as on baseline day 3 and day 3 at high altitude when Hb mass is not measured. On p50 only days, one 2mL blood sample will be taken to measure p50, but no Hb mass measurement will be made.

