Intravenous catheter: Risks associated with placement of an IV include pain and/or bleeding during placement, vasovagal syncope, hematoma (pooling of blood under the skin), infection, and vessel blockage. The placement of the IV may cause some discomfort with rare bleeding or bruising at the puncture site. It also carries the risk of infection. To mitigate risks associated with vasovagal syncope, the subject will be safely positioned upright and sitting in an IV chair, and the subject will be continually monitored by [name] and colleagues, all of whom are trained to place IVs. As such, the **probability** of the adverse reactions discussed above is low, and the **severity** is minimal.

Blood Removal: Risks associated with the removal of blood include an aversion to seeing blood that could result in nausea, vasovagal syncope, increased stress, and/or feeling faint. To mitigate these potential risks, the subject is continually monitored by [name] PhD and colleagues. In addition, the subject is safely and comfortably positioned on a gurney or cot. In this way, the potential risk of vasovagal syncope (i.e., fainting) is mitigated.

A total of ~435-465 mL of blood will be drawn throughout the study. The range up to 465ml is included in case extra samples are required for screening metabolic panels due to abnormalities in findings or compromised samples. Of that volume, 25mL will be drawn baseline day 1 as part of the physical examination. In total, ~162 mL will be drawn prior to departure to Colorado for metabolic panels, biomarker analysis, dried blood spots, Hb mass, and p50. An additional ~213 mL will be drawn during the 2 weeks at high altitude (max volume of ~71mL per day), and ~60 mL will be drawn as part of post-altitude testing. 1 pint of blood, the normal volume of blood donated on a given day, is ~473mL. Throughout the entire study, we will be taking less than that, and the maximum volume for a given day does not exceed ~76 mL. As such, the **probability** of the adverse reactions discussed above is low, and the **severity** is minimal.

The following table is meant to breakdown the volume of venous blood that will be drawn on a given day, as well as what it will be used for:

	Informed consent	Baseline 6	Post Treatment	Altitude 1	Altitude 7	Altitude 13	Post-altitude
Screening panels	25 mL	5mL	None	None	None	None	None
Biomarkers	None	60 mL	60 mL	60 mL	60 mL	60 mL	60 mL
Hb Mass & p50	None	10 mL	None	10 mL	10 mL	10 mL	None

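### Within-arm change in Hb mass is not corrected for the haemoglobin removed by the study's own blood draws, up to about 3.6 to 7.2 percentage points of baseline by altitude day 13 under assumed body sizes

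*Combined protocol and SAP*

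**What the plan says.** Aim 2 (section B) asks how iron and EPO affect "acute and chronic changes in hemoglobin (Hb) mass", among other outcomes. Under the Hb mass and p50 procedure in section C, Hb mass is measured by CO rebreathing as "duplicate tests, at baseline day 6 and on days 1, 7, and 13 at high altitude". The procedure refers to established formulas for Hb mass, then gives equations for red cell volume and blood volume. It accepts a pair of tests that agree within 3%.

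Blood is drawn throughout this period. On baseline day 6: "Total Blood drawn for this day of ~76 mL". During the drug intervention: "After the last dose, subjects will have venous blood drawn (~60 mL) prior to departure to Colorado". Each of altitude days 1, 7 and 13 has a 60 mL biomarker draw and 10 mL for Hb mass and p50. Altitude day 3 has a 2 mL p50 sample. Section G gives the totals: "In total, ~162 mL will be drawn prior to departure to Colorado", "An additional ~213 mL will be drawn during the 2 weeks at high altitude", and overall "A total of ~435-465 mL of blood will be drawn throughout the study".

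Blood removal is discussed only as a risk to participants. Neither the Hb mass procedure nor any other part of the text adds withdrawn haemoglobin back, and the document has no statistical analysis section that could do so.

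**The concern.** Drawing blood removes haemoglobin. If a subject's Hb mass on altitude day 13 is compared with baseline, whatever the study took in between and the body has not replaced appears as a fall in Hb mass, or as a smaller rise. This error runs in one direction, accumulates over days 1, 7 and 13, and does not average out with more subjects.

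The statements at risk are within-arm ones: how much Hb mass rises with acclimatisation in the placebo arm, and the shape of the time course in each arm. Draw volumes are also the same for everyone, so the loss is a larger share in a small subject than in a large one. The plan aims for about half of each sex, so an apparent difference in acclimatisation by sex or body size could be partly an artefact of sampling.

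**Working it through.** **The plan's own totals.** These use the blood table in section G plus the two 2 mL p50-only samples (baseline day 3 and altitude day 3), which the table omits.
- Before departure: 25 + (5 + 60 + 10 + 0.08) + (60 + 0.08) + 2 = 162.2 mL (stated ~162).
- At altitude: 3 × (60 + 10 + 0.08) + 2 = 212.2 mL (stated ~213, which is 3 × 71).
- Post-altitude: 60 mL. Sum 434.4 mL (stated ~435).

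The stated volumes reproduce.

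**Volume removed between the baseline and day-13 tests** (dried spots ignored; together under 1 mL).
- Post-treatment 60 + altitude day 1 70 + day 3 2 + day 7 70 = 202 mL.
- If the baseline day-6 samples (about 75 mL) follow the baseline test: 202 + 75 = 277 mL. The text on day 6 describes the Hb mass test first and the other samples after it, but fixes no order.

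Both figures take the day-13 biomarker draw as following that day's test, which is the order in which the text lists them.

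**Conversion to a share of Hb mass.** Percentage points lost = 100 × volume × Hb concentration / Hb mass. The documents give no Hb mass, Hb concentration or blood volume, so these are assumptions: 500 g at 13 g/dL for a small subject and 900 g at 16 g/dL for a large one. The plan's two equations combine to blood volume = Hb mass / (0.91 × Hb concentration):
- 500 / (0.91 × 0.13) = 4,226 mL, about 4.2 L.
- 900 / (0.91 × 0.16) = 6,181 mL, about 6.2 L.

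| Volume by day 13 | 500 g at 13 g/dL | 900 g at 16 g/dL |
|---|---|---|
| 202 mL | 26.3 g, 5.3% | 32.3 g, 3.6% |
| 277 mL | 36.0 g, 7.2% | 44.3 g, 4.9% |

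Every cell exceeds 3%. The gap between the small and the large subject is 5.3 − 3.6 = 1.7 points at 202 mL and 7.2 − 4.9 = 2.3 points at 277 mL.

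**Time course, and why order matters.** On the lower count the removal is 60 mL by the day-1 test, 60 + 70 + 2 = 132 mL by day 7, and 202 mL by day 13. For the small subject that is 1.6, 3.4 and 5.3 points; for the large one 1.1, 2.3 and 3.6. On altitude day 1 the text lists the biomarker draw before the Hb mass test, but on days 7 and 13 after it. Placing one 60 mL draw before a test instead of after it shifts that visit by 60 × 0.13 / 500 = 1.6 points (small) or 60 × 0.16 / 900 = 1.1 points (large).

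**Against a gain.** The plan states no expected rise. If the true rise were 5% of baseline (assumed) and nothing were regenerated, the observed change would lie between 5 − 3.6 = +1.4% and 5 − 7.2 = −2.2%. For a 10% rise (assumed) it would lie between +6.4% and +2.8%.

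**The case against.** The strongest objection is that Aim 2 concerns the effect of the drugs. Placebo subjects are randomised and undergo the same procedures and draws, so the loss is common to all arms. This stands. A reader might infer that the iron or EPO effect is itself biased to a material degree, and the documents do not support that. If Hb concentration were 10% higher in the EPO arm at every draw (assumed), then at an assumed 5 L blood volume the arms would differ by only 0.1 × 202/5,000 = 0.4 points to 0.1 × 277/5,000 = 0.55 points. Nor do the aims name a comparison of small with large subjects; the named subgroup is PFO status.

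Regeneration is the second objection, and it also stands. Baseline day 6 falls about 30 days before departure, so about six weeks separate the first and last tests. Some of the lost haemoglobin will have been replaced, possibly more under EPO. The figures above are therefore ceilings. For the same reason add-back can over-correct, because replaced haemoglobin is then counted as acclimatisation. Making the adjusted value the sole main result would be a preference that the documents do not justify.

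Third, the Hb mass paragraph describes a measurement, and an analyst might still apply a correction. That is possible, but nothing in the plan commits to one.

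**Conclusion.** The point holds for within-arm change from baseline and its time course. As the plan is written, these are biased downward by up to about 3.6 to 7.2 percentage points of baseline Hb mass at altitude day 13, and by more in smaller subjects. The range rests on assumed body sizes, on planned rather than actual volumes, on the day-13 biomarker draw following the test, and on no regeneration. The randomised contrast with placebo is largely unaffected.

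Two further readings should be avoided. The percentages are shares of total Hb mass; they do not mean that the gain is understated by only that proportion, and as a share of a modest gain the loss could be far larger. And the 213 mL stated for altitude is not the relevant volume: it includes the day-13 draw and leaves out what is taken between the baseline test and departure.

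**What to change.** - Keep the contrast of iron or EPO with placebo as the main Hb mass estimate.
- Fix the order of biomarker draw and Hb mass test, the same at every visit including baseline day 6.
- Log the actual volume and the Hb concentration at each draw, including repeat Hb mass tests and any extra samples.
- Report within-arm change both unadjusted and adjusted, where adjusted Hb mass at a visit = measured Hb mass + the sum, over all draws since the baseline test, of volume × Hb concentration.
- State that the two versions bracket the true change, measurement error aside. Unadjusted change ignores the removal, and add-back ignores regeneration.

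The cost is a volume log and one extra analysis; no procedure is added. Hb concentration should already be available, since the Hb mass tests, the p50 calculation and the dried blood spots all provide it. The documents give only planned, approximate volumes and do not say that actual volumes are recorded for each subject, so the log has to be written into the plan.

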Hb mass measurement: Risks associated with CO determination of blood volume include exposure to carbon monoxide. Most non-smoking city dwellers have 1.5-2.0% CO in their blood and the duplicate tests will increase it to ~15%. The level most commonly associated with symptoms is >15%, with no symptoms reported at 10% or lower. Minor symptoms are present when CO levels rise to 30%. These symptoms may include: confusion, headache, fatigue, nausea, shortness of breath, dizziness, cough, and cherry-colored lips. To protect against an excessive increase in CO we

will only test individuals whose baseline CO level is 3% or less. Further, if an individual's post-CO rises to 20% or higher following the duplicate test we will initiate oxygen therapy. This will have subjects breathe 100% oxygen for 10 min, which reduces the CO half-life from 5 hours to 80 minutes and is the approved therapy used in a clinical setting to treat CO poisoning. In the unlikely event that a subject's CO bound to hemoglobin is excessive and does not appear to be responding to O₂ therapy we will call appropriate police dispatch, depending on the location of the incident (Eugene, OR or Colorado). This method has been in use in research in a wide variety of populations to measure Hb mass including elite athletes (male and female), untrained individuals (male and female), adolescents (11-15 year old boys and girls), elderly subjects, and pregnant women with no ill effects reported. The use of CO as a marker for measuring blood volume has been in use for over 100 years without notable complications. Subjects will be verbally reminded of the symptoms associated with increased carbon monoxide levels prior to their participation in the CO uptake test and will be asked to notify researchers if they are experiencing any of the side effects of carbon monoxide during or after the test.

Altitude associated risks: Staying at high altitude causes systemic hypoxia. This decreased oxygenation can lead to several things depending on how high one goes, how fast one goes there, and how well adjusted to high altitude one is. The consequences can range from mild to severe.

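### The rescue step at HbCO of 20% or higher is a fixed 10 minutes of oxygen, which by the plan's own half-lives lowers 20% only to about 18.3%, with no re-measurement or stopping value given

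*Combined protocol and SAP*

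**What the plan says.** Hb mass is measured by duplicate CO rebreathing on baseline day 6 and on altitude days 1, 7 and 13.

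- **Trigger and treatment, section C (Hemoglobin mass (Hb mass) and p50).** The plan states "CO level in the blood is not expected to exceed 20% following the second test" and continues "If it does, subjects will breathe 100% oxygen for 10 minutes".
- **Trigger and treatment, section G (Hb mass measurement).** The trigger is worded slightly differently: if an individual's "post-CO rises to 20% or higher following the duplicate test we will initiate oxygen therapy". That therapy will have "subjects breathe 100% oxygen for 10 min, which reduces the CO half-life from 5 hours to 80 minutes".
- **Escalation, section G.** If CO bound to hemoglobin "is excessive and does not appear to be responding to" oxygen, staff call police dispatch.
- **Expected level.** Section C puts the rise at about 6 to 8 points per dose. Section G says "the duplicate tests will increase it to ~15" percent.
- **Symptoms.** Both sections associate symptoms with levels above 15%. Section G adds "Minor symptoms are present when CO levels rise to 30" percent. Subjects are "asked to notify researchers if they are experiencing any of the side effects of carbon monoxide during or after the test".

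Neither section gives an HbCO sample after the oxygen, a value at which oxygen may stop, or a definition of response. The 10 mL drawn per session is fully allotted (4 mL for each of the two tests, 2 mL for p50). The spare volume in section G (Blood Removal) is reserved for repeat screening panels. Section G (Emergency Procedures) refers to a separate emergency document that is not in this file.

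**The concern.** The rescue is defined by its duration, not by its result. Ten minutes is one eighth of the stated half-life on oxygen, so little CO can be cleared in that time. A staff member who follows the text exactly could stop oxygen with the subject almost where they started, and for higher starting values still at a level that calls for treatment.

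The escalation rule depends on recognizing that a subject is not responding. If the expected fall is small whether or not oxygen is working, that cannot be recognized at 10 minutes, and no later check is scheduled. At stake is the safety of the few subjects who might ever reach the trigger, in the Eugene lab or at the Colorado field site. No efficacy endpoint or analysis depends on this step.

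**Working it through.** The plan states no HbCO after rescue, so there is no figure of its own to reproduce. The check applies its half-lives to its own trigger.

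**Inputs.** Trigger 20%, duration 10 min, and half-life 80 min on oxygen and 300 min in air (section G, Hb mass measurement). Baseline 1.5-2.0%, with an upper limit of about 3% (sections G and D). Rise per dose 6-8, read as percentage points (section C).

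**Formula.** HbCO(t) = HbCO(0) × 2^(−t / half-life). The 80-minute half-life is taken to apply only while oxygen is being breathed.

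| From 20% | On oxygen | In air | Gap |
|---|---|---|---|
| 10 min | 20 × 2^(−10/80) = 18.34% | 20 × 2^(−10/300) = 19.54% | 1.20 points |
| 30 min | 20 × 2^(−30/80) = 15.42% | 20 × 2^(−30/300) = 18.66% | 3.24 points |

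Ten minutes of oxygen removes 8.3% of the load, and ten minutes of air removes 2.3%.

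**Start that is still at the trigger after 10 min of oxygen.** 20 / 2^(−10/80) = 21.8%.

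**Time on oxygen from 20% to 15%.** 80 × log2(20/15) = 33 min. If oxygen stops at 10 minutes, reaching 15% takes a further 300 × log2(18.34/15) = 87 min in air.

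**Sensitivity: only the excess over baseline decays.** HbCO(t) = b + (20 − b) × 2^(−t / half-life). For b = 1.5, 2 and 3%:

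- after 10 min of oxygen: 18.46, 18.51 and 18.59%
- after 10 min of air: 19.58, 19.59 and 19.61%, so the gap shrinks to 1.0-1.1 points
- start still at the trigger: 21.67, 21.63 and 21.54%
- time to 15% on oxygen: 36, 38 and 40 min

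**Is 20% likely to be reached?** With no washout, two doses give 1.5 + 2×6 = 13.5% up to 2 + 2×8 = 18%, or 3 + 2×8 = 19% from a 3% baseline. Washout before the second dose lowers these. Four minutes of oxygen leaves 2^(−4/80) = 0.966, and with 10 minutes of air as well 0.944, so the low end is (1.5 + 6) × 0.944 + 6 = 13.1%. Reaching 20% needs between (20 − 3)/2 = 8.5 points per dose (3% baseline, no washout) and (20 − 1.5×0.944)/1.944 = 9.6 points per dose (1.5% baseline, full washout), against the stated 6-8.

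**The case against.** The strongest reply is that the trigger lies outside what the plan's inputs produce, and that the step does what it needs to do. A subject who falls from 20% to 18.3% is back among the levels of 18-19% that the plan leaves untreated after routine testing. This holds for any start up to about 21.5-21.8%. To finish above the trigger, a subject would need roughly (21.8 − 3)/2 = 9.4 points per dose even from a 3% baseline with no washout. This stands, and it is the main reason why the point is minor.

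Second, the plan is not silent on response. The escalation clause presupposes some assessment after oxygen. Section G (Emergency Procedures and the equipment list before it) refers to AHA and ACLS guidelines for giving oxygen in the lab. Section G (Altitude associated risks) requires an emergency call for severe symptoms in Colorado, and investigators ask subjects how they feel throughout. All this stands as partial cover, but none of it sets an HbCO re-check or a stopping value. Symptoms are also a weak guide in the field. Hb mass is measured on the first evening at altitude, when the plan expects about half of subjects to have symptoms of acute mountain sickness, and headache and nausea or an upset stomach belong to both conditions.

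Third, any particular target or non-response cut is a reviewer's choice. A 15% target would hold a rescued subject to a stricter level than an untreated one at 19%. This stands too, so the values under the fix are examples for the investigators to replace.

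A reader might infer that routine duplicate testing pushes subjects past 20%, or that subjects are knowingly left at a dangerous level with no follow-up. The documents support neither. The expected range is about 13-19%, section G places minor symptoms at 30%, and a route for escalation exists.

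**Conclusion.** The point holds as a minor defect in a contingency step. Followed exactly, the fixed 10 minutes lowers 20% to about 18.3% (18.5-18.6% if only the excess over a 1.5-3% baseline decays), against about 19.5-19.6% in air. The level at the end is still above the 15% that the plan links with symptoms. Starts above about 21.5-21.8% end over the trigger. The escalation rule cannot work at 10 minutes because oxygen and air differ by only 1.0-1.2 points. That this is too small to act on is a judgment, since the plan states no precision for the HbCO reading.

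The result rests on simple first-order decay with the plan's two half-lives. The arithmetic is firm. The absence of a re-check is firm only for this file, because the separate emergency document could not be read and may already supply it.

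**What to change.** In section C (Hemoglobin mass (Hb mass) and p50) and section G (Hb mass measurement):

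1. Replace the fixed 10 minutes with 100% oxygen continued until a re-measured HbCO is below a value set by the investigators.
2. Take the first re-measurement at about 30 minutes, when a start of 20% should be near 15.4% on oxygen and near 18.7% in air.
3. Define non-response and escalate then as section G already says. One example is HbCO still above 85% of its starting value at 30 minutes. The midpoint of the two curves is (15.42 + 18.66)/2 = 17.04, or 85% of 20. Oxygen should leave 77% of the starting value and air 93%, or about 80% and 94% if only the excess over a 3% baseline decays.
4. Use one trigger, 20% or higher, in both sections.

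If the separate emergency document already covers this, a cross-reference and matching wording are enough.

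**Cost.** The change takes a few sentences and, rarely, about 30-40 minutes of oxygen in place of 10. Oxygen is already available at both sites, and the IV and HbCO measurement are already part of the test. Each re-measurement takes about 2 mL. A 15% target needs at least two samples, because about 15.4% is still expected at 30 minutes. Baseline day 6 would then rise from 5 + 60 + 10 + 0.08 = 75.08 mL to 77.08 mL with one sample or 79.08 mL with two (stated maximum about 76). Altitude days would rise from 60 + 10 + 0.08 = 70.08 mL to 72.08 or 74.08 mL (stated about 71). Section G (Blood Removal) should allow for this.
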